# **Experimental Design**

#### 1. Object

To evaluate the safety and efficacy of biologic hollow bone screws for the fixation of fractures in knee joint and ankle joint.

#### 2. Experimental Method

According to the Guiding Principles for Clinical Trial Design of Medical Devices, a prospective, multicenter, randomized, single-blind, parallel-controlled clinical trial was designed, and the comparison type was non-inferior design.

**Randomization Method:** Subjects will be enrolled in this clinical trial after signing informed consent and meeting the inclusion criteria but not the exclusion criteria. The sample size and block length were set using the system generation or a seed number specified by the randomizer. The random number table required for the test was generated by the PROC PLAN process, and the random number table was introduced into the random system. According to the random system grouping, the subjects were randomly assigned to the experimental group or the control group, and the ratio of the experimental group and the control group was 1:1.

**Masking (Single):** The researchers can visually distinguish the experiment products and the control products, so the researchers cannot be blinded and the participants were blinded.

**Non-Inferior Design:** The control product is a marketed device whose efficacy/safety has been recognized, so the non-inferior design is used. If the difference in efficacy/safety between the test device and the control device is less than the pre-set non-inferiority threshold, the difference is within the clinically acceptable range.

Selection of Reference Products: At present, there is no biological bone hollow screw with the same principle and material in China. According to the Guiding Principles for Clinical Trial Design of Medical Devices, priority should be given to commercially available similar products whose efficacy and safety have been clinically recognized when selecting positive controls. And if reasonable reasons cannot be used for similar products already on the market, a product as similar as possible can be used as a positive control. Therefore, the absorbable screw (Inion Freedom Screw) developed by Inion Oy, Finland, was selected as the control product in this clinical trial.

#### 3. Measures to Reduce and Avoid Bias

**Investigator Training:** Before the start of the clinical trial, the supervisor and the principal investigator of each trial center should train the investigators on the trial protocol and product use, so that the investigators can understand and master the trial products, trial protocol and process.

Clinical Trial Monitoring: The sponsor will appoint an auditor to

conduct regular on-site monitoring visits to the trial hospital to ensure that all aspects of the study protocol are strictly adhered to, and the CRF will be checked to ensure that the content is consistent with the original data.

# 4. The Diagnosis and Treatment Methods of Experimental and Control Medical Devices

#### 4.1 Instructions for the Installation and Use of Experimental Devices

According to the specific conditions of each patient, the selection of the appropriate model and size of the implant is an important factor affecting the success rate of surgery. After implantation, the implant will be in a repetitive stress environment for a long time, so attention must be paid to patient selection, proper placement of the implant, postoperative care and functional rehabilitation to minimize the stress on the implant, otherwise such stress may lead to material fatigue and subsequent fracture, bending or loosening of the implant before bone healing is achieved. This can cause damage or require early removal of the implant.

#### 4.2 Before Surgery

(1) Only those patients who meet the indication criteria should be selected.

(2) The condition described in the contraindications section above should be avoided.

(3) In the process of transportation and storage, avoid collision, scratches

or other forms of damage to the implant. Special care should be taken to make the storage environment of the implant.

(4) The surgeon should be familiar with the use of this product and its supporting instruments before use, and confirm that they are ready before the operation.

(5) The type of implant that should be used in each surgical patient and the approximate size range should be determined before the operation begins. A sufficient number of implants of various sizes should be prepared for surgery, including those larger and smaller than expected.

(6) Unless packaged in sterile form, all instruments should be cleaned and sterilized prior to use.

#### 4.3 During Surgery

(1) For Easy and Safe Screw Insertion:

A. The fracture site should be anatomic reduction or functional reduction. The 1.2mm Kirchner needle should be drilled to the required depth, and the nail path should be established along the Kirchner needle using a hollow drill.

B. Insert the appropriate size tap along the Kirschner needle to form the thread path. The size is consistent with the intended screw length. Screw in to the same depth as the corresponding screw length. Screw into the appropriate depth, counterclockwise out of the tap.

C. Select the appropriate size of the bio-type bone hollow screw and

press the screw head into the tail of the screw to ensure that the whole screw can be picked up. Screw along the Kirschner needle until complete implantation into the bone. The screw and screw are kept parallel to the direction of the bone.

(2) Ensure aseptic operation during the surgery.

(3) Peripheral nerves and blood vessels should be protected during operation.

(4) Breakage, slip or misuse of an instrument or implant during implantation may result in injury to the patient or the surgery.

(5) For more detailed surgical instructions, please refer to the appropriate surgical technical literature.

#### 4.4 After Surgery

(1) The physician should provide the patient with a detailed description of the limitations of the product. Patients should be warned that complications such as bending, loosening or breaking of the implant may be caused by excessive weight bearing, excessive muscle activity or sudden impact on the surgical site. Patients should be told how to limit and control physical activity and advised to avoid strenuous exercise and excessive weight bearing.

(2) During the healing stage of the fracture, the physician should advise the patient not to smoke or drink too much alcohol.

(3) It is very important to confirm whether bone healing occurs after the

operation by X-ray. Bone non-union or delayed healing during the treatment stage will cause the implant to be subjected to repeated stress for a long time, which may fatigue the product and eventually bend, loosen or fracture. Therefore, if non-healing occurs or if the implant is loose, bent or broken, the implant should be adjusted or removed when serious damage is imminent.

(4) Any removed implants should be properly disposed of to ensure that the product will not be used in other surgeries.

# **4.5 Control Instrument Operation Methods**

The operation was carried out by professional doctors participating in this clinical trial according to the instructions.

Items	Experimental Device	Control Device
Name	Biologic Hollow Bone Screws	Inion Freedom Screws
Туре	SL30, SL32, SL34, SL36, SL38, SL40, SL42, SL44, SL46, SL48, SL50	Diameter :3.5mm/4.5mm Type: Hollow screw
Main Components	The product is made of silk fibroin protein, and the degradation products are amino acids and peptides, which are harmless to human body. The structure includes head thread, tail thread, rod part and hollow hole. The screw is a double-headed compression screw to achieve compression fixation at both ends of the fracture. It is hollow structure, which is not only easy to guide needle through, but also conducive to bone trabecular growth. Co60 irradiation	The product consists of an absorbable screw (L-lactic-D mixed with L-lactic acid copolymer) and a metal adapter (auxiliary screw screwing without contact with the human body). Made of 316 stainless steel according to ASTM F899 standard. Sterilized
	sterilization package.	

#### **4.6 Product Information**

Application	Used for fixation of fractures of the knee joint and ankle joint	Used in conjunction with suitable auxiliary fixation, such as a strong fixation implant, cast, or brace,
		intended for reduction of a fracture
		during fracture healing Maintain.
Source	Jiangxi Sike Biotechnology Co., LTD	Inion Oy Company, Finland.
Registration	NA	NationalMedicalDeviceRegistration:20153130029
Number		

# 5. Subject Selection

# 5.1 Inclusion Criteria

(1) Aged 18-75 years old (inclusive), both sexes;

(2) Patients with knee and ankle fractures requiring internal fixation confirmed by imaging examination;

(3) Voluntary participation in the clinical trial and signing of the informed consent.

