### 5.2 Exclusion Criteria

(1) The following conditions exist at the fracture site: infection, osteofascial compartment syndrome, osteitis, pathological fracture, open fracture, severe tissue or vascular and nerve injury, or insufficient bone mass of the affected limb affecting screw implantation, etc.

(2) Abnormal liver and kidney function with clinical significance (ALT,

AST 2 times the upper limit of normal value and Cr 2 times the upper limit of normal value);

(3) Abnormal coagulation function with clinical significance (APTT > 2

times the upper limit of normal value);

(4) Patients with difficult-to-control diabetes (any blood glucose > 11.1mmol/L or glycosylated hemoglobin > 9%);

(5) Past allergies to silk protein materials;

(6) Mental illness;

(7) Patients who cannot guarantee to quit smoking during the fracture healing period;

(8) Pregnant or lactating women or women of childbearing age who plan to get pregnant within 6 months;

(9) Those who have participated in other pre-clinical trials within 1 month before the trial;

(10) Those who are considered inappropriate to participate in the clinical trial.

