#### 5.3 Remove Criteria

(1) No devices were used after enrollment.

(2) Violation of inclusion or exclusion criteria.

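### Suitability for either study screw is not confirmed before randomisation, so it can be judged with the arm known and non-use can differ by arm

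*Protocol*

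**What the plan says.** Fracture eligibility rests on inclusion criterion 5.1(2): "Patients with knee and ankle fractures requiring internal fixation confirmed by imaging examination". Among the exclusions, 5.2(1) lists several fracture-site conditions, including "insufficient bone mass of the affected limb affecting screw implantation", and 5.2(10) is a catch-all: "Those who are considered inappropriate to participate in the clinical trial". None of these refers to available screw sizes or to suitability for both products.

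The table under Protocol 4.5 describes the test screw by model code ("SL30, SL32, SL34, SL36, SL38, SL40, SL42, SL44, SL46, SL48, SL50") and the control by diameter ("Diameter :3.5mm/4.5mm").

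Sizing appears in 4.2(5), within the instructions for the test device: "The type of implant that should be used in each surgical patient and the approximate size range should be determined before the operation begins". The same item asks for a stock that includes sizes above and below those expected. Control operations simply follow the control product's own instructions (4.5).

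On sequence, the Trial Procedure places X-ray and the eligibility decision at screening (2.1, items 14 and 15) and grouping on the day of surgery (2.2, item 2). Section 2 of the Experimental Design states that researchers can see which product they hold and cannot be blinded. Section 5.6 makes randomisation the moment of enrolment. Section 5.3(1) then lists as a ground for removal: "No devices were used after enrollment".

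SAP section 9 forms the FAS by eliminating subjects from all those enrolled but lists no reasons. The heading of SAP section 7 covers dropouts and missing data, but the text beneath it gives no rule for them.

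**The concern.** A randomised comparison of two implants is cleanest when everyone randomised could have received either one, and when that judgement was made without knowledge of the arm. Here a site can follow the plan exactly and still decide on suitability after allocation, with the surgeon aware of the product. If the allocated screw is then judged unsuitable, the subject meets a removal criterion.

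Two things could follow. If such subjects stay in the analysis as not healed, an arm is penalised for something other than failed healing. If they are removed, the comparison depends on who was removed. A surgeon who sets aside the harder fractures in one arm only changes the prognosis of that arm.

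**Working it through.** **Inputs.** Healing 95.5% in control and the same assumed for test; margin -10%; two-sided alpha 0.05; power 0.80 (SAP section 3.A). Dropout up to 15% (SAP section 4). 80 per arm (Protocol 5.9). Success if the 95% CI lower limit for test minus control exceeds -10% (SAP section 5).

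**The plan's own figure.** n = (1.96 + 0.8416)² × [2 × 0.955 × 0.045] / 0.10² = 67.46, rounded up to 68 per arm. 68 / 0.85 = 80 per arm, 160 in all. Both stated numbers reproduce. The dropout allowance has no slack, since 80 × 0.85 = 68.

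**Assumed illustration.** 0.955 × 80 = 76.4, so take 76/80 healed in each arm as the reference. Let k test-arm subjects who would have healed receive no device, with no such losses in control. The documents give no value for k and do not name a CI method, so two were used:

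- Wald: lower limit = d - 1.96 × √[pT(1 - pT)/nT + pC(1 - pC)/nC]
- Newcombe: lower limit = d - √[(pT - lT)² + (uC - pC)²], with Wilson limits l and u

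Worked example, k = 3 counted as not healed: pT = 73/80 = 0.9125, pC = 0.95, d = -0.0375, SE = √(0.000998 + 0.000594) = 0.0399, so the Wald limit is -0.0375 - 0.0782 = -0.1157.

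| k | Counted as not healed | Wald | Newcombe | Removed | Wald | Newcombe |
|---|---|---|---|---|---|---|
| 0 | 76/80 | -6.75% | -7.78% | 76/80 | -6.75% | -7.78% |
| 1 | 75/80 | -8.39% | -9.40% | 75/79 | -6.86% | -7.92% |
| 2 | 74/80 | -9.99% | -10.98% | 74/78 | -6.97% | -8.06% |
| 3 | 73/80 | -11.57% | -12.52% | 73/77 | -7.08% | -8.21% |
| 4 | 72/80 | -13.13% | -14.04% | 72/76 | -7.19% | -8.36% |

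Counted as not healed, the rule fails from k = 2 (2.5% of the arm) by Newcombe and from k = 3 (3.8%) by Wald. With k = 2, Wald still just passes. Removed, every row passes.

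**Chance of success** by exact binomial enumeration, 95.5% healing in both arms, Wald (Newcombe):

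- no losses: 0.85 (0.78)
- counted as not healed: k = 2, 0.58 (0.46); k = 3, 0.41 (0.29)
- removed, unrelated to healing: k = 4, 0.85 (0.73); k = 8, 0.82 (0.70)

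**Removal related to prognosis.** Put the true test rate at the margin, 95.5% - 10% = 85.5%, and remove from the test arm 3 subjects who would not have healed. The chance of wrongly declaring non-inferiority rises from 0.038 to 0.18 (Wald) or from 0.025 to 0.14 (Newcombe). This is a deliberately adverse case, because every removal is a would-be failure.

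**The case against.** The plan has partial safeguards. Section 5.2(1) excludes open and pathological fractures, severe soft-tissue or neurovascular injury and inadequate bone mass, and its list is open-ended. Section 5.2(10) lets the investigator decline anyone unsuitable. Section 4.2(1) confines use to patients who meet the indication, and 4.2(5) requires pre-operative sizing and spare sizes. The screening X-ray precedes the eligibility decision, and SAP section 3.B says subjects are screened against the test device's scope of application, with specific diseases deliberately left unrestricted. All of this stands and makes non-use less likely. None of it calls for a judgement on both devices before allocation.

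A reader might infer from the table in 4.5 that the two ranges differ and that some fractures fit only one product. The documents do not support that. They give no control lengths, no test diameter and no meaning for the SL codes, so the difference may be only in how the ranges are described. A reader might also infer that any knee or ankle fracture can be randomised unchecked; the exclusions and the sizing step rule that out.

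The change of verdict in the table also depends on counting unfitted subjects as failures, which neither document prescribes, and on all losses falling in one arm. With 2 lost in each arm and counted as not healed (74/80 against 74/80), the limits are -8.2% (Wald) and -8.9% (Newcombe), a pass. Finally, surgeon unblinding is inherent to these devices. That is fair, but it is a reason to fix the plan before the arm is known.

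**Conclusion.** The point holds as a gap in sequence: the plan does not require a suitability judgement covering both devices before randomisation, and it provides for removing randomised subjects who got no device. Non-use can therefore depend on the arm.

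Its size is conditional. Two to three losses in one arm of 80 separate a pass from a fail, but only if they count as not healed. Simple removal unrelated to healing barely matters. The real bias risk is removal linked to prognosis. These figures rest on an assumed k, an assumed split between arms, 95.5% healing (85.5% for test in the false-positive case) and a CI method that the SAP does not name.

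It would go too far to say that size mismatch will decide this trial: neither a mismatch nor a non-fit rate can be shown from the documents. The change is still worth making, because it is cheap and acts before bias can arise.

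**What to change.** Add to 5.1, and place ahead of the grouping step in Trial Procedure 2.2, for all subjects: before randomisation the surgeon records from the screening images the planned screw position, number and size, and confirms that the fracture can be treated with a suitable size of either study device.

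Pair this with SAP section 9: keep all randomised subjects in the FAS by assigned arm, state how the 24-week outcome is set for those who received no device, align Protocol 5.3(1) with that rule, and report non-use by arm and reason.

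The sample size stays at 68 evaluable per arm and 160 in total. The cost is one eligibility line and one eCRF item, using an X-ray already taken and extending to both arms the planning that 4.2(5) already asks for. The downside is that a few patients suited to only one product are not enrolled.

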### 5.2 Exclusion Criteria

(1) The following conditions exist at the fracture site: infection, osteofascial compartment syndrome, osteitis, pathological fracture, open fracture, severe tissue or vascular and nerve injury, or insufficient bone mass of the affected limb affecting screw implantation, etc.

(2) Abnormal liver and kidney function with clinical significance (ALT,

AST 2 times the upper limit of normal value and Cr 2 times the upper limit of normal value);

(3) Abnormal coagulation function with clinical significance (APTT > 2

times the upper limit of normal value);

(4) Patients with difficult-to-control diabetes (any blood glucose > 11.1mmol/L or glycosylated hemoglobin > 9%);

(5) Past allergies to silk protein materials;

(6) Mental illness;

(7) Patients who cannot guarantee to quit smoking during the fracture healing period;

(8) Pregnant or lactating women or women of childbearing age who plan to get pregnant within 6 months;

(9) Those who have participated in other pre-clinical trials within 1 month before the trial;

(10) Those who are considered inappropriate to participate in the clinical trial.

#### 5.3 Remove Criteria

(1) No devices were used after enrollment.

(2) Violation of inclusion or exclusion criteria.

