#### 5.6 Group Entry Time

After signing the informed consent form, meeting the inclusion criteria and not meeting the exclusion criteria, the time when the subject underwent randomization was the enrollment time.

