# **Trial Procedure**

#### 2.1 Screening Period (V0 period: -7-0 days)

Informed consent must be signed prior to any trial-related procedure, after which subjects are assigned a unique screening number that remains unchanged throughout the trial. If the subject is undergoing elective surgery, it is at the discretion of the investigator whether to re-examine the subject if the preoperative examination exceeds the acceptable time range.

(1) Sign informed consent;

(2) Demographic data: gender, age, height, weight;

(3) Complete medical history: previous disease history within 3 months before signing the informed consent, drug use history, smoking history, drinking history, surgical history and allergy history within 1 month;

(4) Vital signs: body temperature, respiration, heart rate, blood pressure;

(5) Blood pregnancy test: only applicable to women of childbearing age;

(6) Bone mineral density examination (test site);

(7) Blood glucose test: including blood glucose and glycated hemoglobin, only for diabetic patients;

(8) Coagulation function test: prothrombin time (PT), activated partial thromboplastin (APTT), fibrinogen (FIB), thrombin time (TT);

(9) Blood routine: hemoglobin (HB), red blood cell count (RBC), white blood cell count (WBC), platelet count (PLT), hematocrit (Hct);

(10) Urine routine: urinary white blood cells (WBC), urinary protein(PRO), urinary red blood cells (RBC), urinary glucose (GLU);

(11) Blood biochemistry: creatinine (Cr), Urea nitrogen (BUN) / Urea, alanine aminotransferase (ALT), aspartate aminotransferase (AST);

(12) C-reactive protein;

(13) Infectious disease examination: HBSAg, HBsAb, HBeAg, HBeAb,

HBcAb, HCV-rna/ HCV-antibody, syphilis TPPA, HIV antibody;

- (14) X-ray examination;
- (15) Determine the inclusion and exclusion criteria;
- (16) VAS score;
- (17) Recording device defects;
- (18) Record drug combination.

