#### 2.2 Day of Surgery (Stage V1: Day 0)

- (1) Vital signs: body temperature, respiration, heart rate, blood pressure;
- (2) Random grouping;
- (3) Record surgical information;
- (4) Instrument performance index;
- (5) Recording device defects;
- (6) Record adverse events;
- (7) Records of combined drug use (except glucose, normal saline and

narcotic drugs);

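### Do the removal grounds in Protocol 5.3 let randomised subjects be dropped selectively from the non-inferiority analysis?

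*Protocol*

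**What the plan says.** Protocol 5.3 lists two grounds and nothing else: "No devices were used after enrollment" and "Violation of inclusion or exclusion criteria". Protocol 5.6 fixes enrolment at allocation: "the time when the subject underwent randomization was the enrollment time". The visit schedule places "Random grouping" on the day of surgery (Trial Procedure 2.2). Protocol 2 says that investigators can tell the devices apart and that only participants are blinded.

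Eligibility is settled earlier. At the screening visit (Trial Procedure 2.1) the investigator is to "Determine the inclusion and exclusion criteria", and the same list includes "Bone mineral density examination (test site"). Most criteria in Protocol 5.2 are factual. Three are looser: exclusion (1), which ends "insufficient bone mass of the affected limb affecting screw implantation, etc"; exclusion (7), on stopping smoking during healing; and exclusion (10), "Those who are considered inappropriate to participate in the clinical trial".

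SAP 9 does not refer to Protocol 5.3. It describes the FAS as close to the intention-to-treat ideal, reached by removing as few enrolled subjects as can be justified. It describes the PPS as those who complied, judged among other things on treatment received and freedom from significant violations. SAP 5 sets success as a lower 95% limit above -10% and names no set.

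**The concern.** A rule that removes subjects after allocation can undo randomisation, and here the people applying it know the arm. Section 5.3 does not say whether a removed subject leaves the FAS, the PPS or follow-up. It does not confine violations to facts known before randomisation, and it asks for no decision masked to arm and outcome. Exclusions (7) and (10) and the open end of (1) could in principle be judged again once healing is known.

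Events are few. At the planned 95.5% healing, 80 × 0.045 = 3.6 non-healings are expected per arm, so a single removal could move the lower limit across -10%. A false claim of non-inferiority would be at stake.

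**Working it through.** **1. The plan's own figure.** Inputs from SAP 3: healing 95.5% in both arms, margin 10 points, two-sided α 0.05, β 0.20. Per arm, n = (1.960 + 0.842)² × 2 × 0.955 × 0.045 / 0.10² = 67.46, so 68. With 15% dropout (SAP 4), 68 / 0.85 = 80. Both match the plan, so the sample size is not in question.

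**2. The two grounds against SAP 9.**

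| Protocol 5.3 ground | When the fact is fixed | Where SAP 9 deals with it |
|---|---|---|
| (1) no device used | at surgery, before any week-24 result | treatment received (PPS) |
| (2) eligibility violation | screening visit, for most criteria | significant violations (PPS) |

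Ground (1) may differ by arm but cannot be decided on week-24 healing. Ground (2) can respond to healing only if eligibility is judged again later, and for most criteria the screening record stands in the way.

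**3. False-claim rate.** Method: enumerate both binomials exactly and count success when the lower 95% limit of test minus control exceeds -10%. Truth is set at the margin: test 85.5%, control 95.5%. All 80 per arm are taken as evaluable. The SAP does not state the interval method, so two are shown. All removal rates are assumptions. Expected unhealed in the test arm: 80 × 0.145 = 11.6.

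| Scenario | Wald | Newcombe |
|---|---|---|
| No removal, 80 v 80 | 3.78% | 2.50% |
| Unrelated to healing, 76 v 76 | 3.61% | 2.42% |
| Unrelated, test arm only, 76 v 80 | 3.78% | 2.10% |
| 5% of unhealed test subjects removed (0.6) | 4.88% | 3.17% |
| 10% (1.2) | 6.36% | 4.17% |
| 30% (3.5) | 18.42% | 12.54% |
| 10% of unhealed, both arms | 5.38% | 3.39% |
| 30% of unhealed, both arms | 12.97% | 7.52% |

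The Wald rate is above 2.5% with no removal at all, so part of every Wald figure belongs to the interval method.

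**4. Can one removal decide the trial?** At equal 95.5% healing, removing one unhealed test subject turns failure into success in 6.76% (Wald) or 7.47% (Newcombe) of trials. In that setting the product truly is non-inferior, so each flip corrects a wrong failure. At the margin, where a flip is a false claim, the figures are 2.74% and 1.59%.

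**5. What the stricter rule would cost.** Suppose subjects without a device stay in the FAS with their observed healing, and a fraction f of the test arm has no screw and heals at the control rate. Then the true test rate is (1 − f) × 0.855 + f × 0.955.

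| f (assumed) | Test rate | Wald | Newcombe |
|---|---|---|---|
| 0 | 85.50% | 3.78% | 2.50% |
| 2.5% | 85.75% | 4.24% | 2.82% |
| 5% | 86.00% | 4.77% | 3.18% |

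At f = 5% this is about the same inflation as removing 5% of unhealed test subjects.

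**6. Power.** At equal 95.5%, power is 85.4% / 77.5% (Wald / Newcombe) with 80 per arm and 84.5% / 74.3% with 76. With 79 per arm it is 84.2% / 73.3%, lower than with 76, so the contrast largely reflects the discreteness of the binomial and does not argue for either rule.

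**The case for a change.** The strongest case for a change is that three gaps are plain in the text. Section 5.3 names no set, sets no time limit on what counts as a violation, and has nobody masked to arm and outcome deciding. SAP 9 lets subjects be eliminated from the FAS without listing the grounds. Section 5.3 is the only removal list in the documents, so a reader might apply it there. The denominator of the healing rate in Protocol 6.2.1 is not defined either, so two analysts could work from different totals. The protocol itself foresees ineligible subjects being enrolled (Feasibility Analysis (2)). Re-signing changed data documents a change but does not prevent it, and the joint signature at database lock is not a masked review. A subject without a device, or with bone found too weak at operation, may also differ in prognosis, so removal might be linked to healing without anyone intending it. The documents give nothing from which to size that.

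The gaps are real as gaps in wording. What does not follow is that the plan yields a wrong result. To do harm, a discretionary criterion must be judged again in the light of non-healing, or removal must be strongly prognostic, and the subject must then leave the set that decides success. No passage directs either step. SAP 9 points the other way on the second, and SAP 7A requires a count of enrolled and completed cases and a list of those dropped, so removals can be seen. The largest figures, 18.4% and 12.5%, need about 3.5 of 11.6 unhealed test subjects to be removed, which nothing in the documents supports.

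**Conclusion.** The concern does not call for a change. Section 5.3 leaves unsaid which analysis set it touches, and SAP 9 supplies a workable answer: keep the FAS close to all randomised subjects and handle both grounds in the PPS. On that reading the FAS result is unaffected by 5.3. Even if a few subjects were removed for reasons unrelated to healing, the false-claim rate at the margin would stay at or below its no-removal value of 3.8% (Wald) or 2.5% (Newcombe). Inflation appears only under assumed removal linked to healing: 4.9% / 3.2% if 5% of unhealed test subjects go, and 6.4% / 4.2% if 10% go.

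A mandatory rule keeping every subject without a device in the FAS as observed would be a trade-off and not a clear gain, because it pulls the arms together in a non-inferiority comparison (up to 4.8% / 3.2% at an assumed 5% without a screw).

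The conclusion rests on 80 evaluable per arm, the planned 95.5% control rate and eligibility being recorded at screening as scheduled. It covers the removal grounds only. Which set decides the -10% criterion, and which interval method is used, are separate questions.
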